#### 3.2.3 Sampling criteria for case/control studies (objectives 1.3)

#### 3.2.3.1 Inclusion criteria

The study will collect data on cases/controls identified during the sample collection study (section 3.1 above)

- 1. Any patient who had a sample sent to the European coordinating laboratory and was positive for CDI (GDH positive/toxin positive) at the European coordinating laboratory
- 2. A matched (age/gender) patient from the same participating site as a patient in criteria 1, but that had a negative result for CDI at the European Coordinating Laboratory.

#### 3.2.3.2 Exclusion criteria

None

#### 3.2.4 Study methods

All CDI positive cases (as determined by the ECL), and a proportion of negative cases (at a ratio of 1 case to 3 controls) will have clinical data collected (after 6 months) on participant outcomes. Data will be compared to identify differences between countries and healthcare providers.

#### 3.2.5 Sample size

We estimate, based on previous experience (please see section on sample size in 3.1.4), that we would receive 480 *C. difficile* toxin positive samples over the two sampling days. These would form the cases for the case/control study. Controls (participants with *C. difficile* negative samples submitted during O1.1) would be recruited at a rate of 1:3, from the same participating centre. Where possible these will be age and gender matched. Given that we will only have a predefined group of participants to select from; it is possible that we are unable to completely match all controls, apart from at the geographical level.

#### 3.2.6 Data collection

Data will be collected via a standardised CRF, with a full supporting SOP. The CRF will be completed by the clinical care team at the participating site that submitted the sample (during O1.1). The CRF will not contain any participant identifiable data; all data will be held against a pseudoanonymised study code, with the link back held by the clinical care team only. COMBACTE-CDI investigators will not access participant's notes or access the link back. Once the CRF data has been collected and validated and verified the link-back will be destroyed by the local study site.

Data will be collected on the following variables on outcomes of CDI;

- Evidence of other enteric pathogens (+/- 7 days of the original sample)?
- Symptoms at time of the sample
- Alternative cause for the patient's diarrhoea documented (e.g. laxatives, pathogen)?
- Duration of diarrhoea/non-normal bowel habit?
- Primary/recurrent CDI
- Antibiotics at the time of the sample or the preceding 3 months?
- Evidence of colitis?
- Evidence of post-infectious diarrhoea

- CDI Severity markers (Temperature (nearest reading +/- 3 days of the sample), serum creatinine (nearest reading +/- 3 days of the sample), White cell count (nearest test +/- 3 days of the sample)
- Treatment for CDI episode
- Was treatment for CDI/diarrhoea escalated medical/surgical?
- Outcome 30 days and 6 months after the sample (discharged, in-patient, died)
- Length of stay

#### 3.2.7 Data analysis

Comparisons will be made between recurrence/Morbidity/Mortality (crude and attributable) rates in different healthcare settings and countries. Outcomes will also be compared for different strain types (as identified in O1.2).

# 3.3 Case control study- objective 1.4 (risk factors)

#### 3.3.1 Study rationale

Many studies have examined risk factors associated with CDI; there are, however, three major deficiencies of existing data; (1) most studies have been performed in the epidemic setting and so may be biased by a preponderance of cases caused by one or a few strain types; (2) most studies are in hospitalised patients; (3) most were biased to patients receiving antibiotics, identified antibiotic use as the most important risk factor, and so reduced the potential to identify other modifiable risk factors. Conversely, several studies have shown that exposure to prescribed antibiotics was not present in up to 50% of CA-CDIs. CA-CDI, therefore, may be linked to other microbiota disturbing factors (other drugs, diet, etc.) currently not recognised as risk factors for CDI. Recent data have questioned whether PPIs are truly associated with CDI; earlier results may be confounded by choice of control patients.

A recent systematic review of risk factors associated with CDI recurrence and mortality noted that important variables were inconsistently reported, such as previous episodes and antibiotic use. Also, there was substantial heterogeneity and methodological limitations, including sample sizes, definitions of outcomes and follow-up periods, thus precluding a meta-analysis. We have considerable experience of determining risk factors associated with CDI. Notably, a recent University of Leeds study has determined CDI risk factors for cases determined according to a standardised diagnostic algorithm (data unpublished).

#### 3.3.2 Outcome measures

Primary outcome measure: Episode of CDI

#### 3.3.3 Sampling Criteria for sample collection study (objective 1.4)

#### 3.3.3.1 Inclusion criteria

The study will collect data on cases/controls identified during the sample collection study (section 3.1 above)

- 1. Any patient who had a sample sent to the European Coordinating Laboratory and was positive for CDI (GDH positive/toxin positive) at the European Coordinating Laboratory
- A matched (age/gender) patient from the same participating site as a patient in criteria
  but that had a negative result for CDI at the European Coordinating Laboratory.

# *3.3.3.2 Exclusion criteria* None

#### 3.3.4 Study methods

All CDI positive cases (as determined by the ECL), and a proportion of negative cases (at a ratio of 1 case to 3 controls) will have clinical data collected (after 6 months) on possible risk factors for CDI. Data will be compared to identify differences between countries and healthcare providers.

#### 3.3.5 Sample size

We estimate, based on previous experience (please see section on sample size in 3.1.4), that we would receive 480 *C. difficile* toxin positive samples over the two sampling days. These would form the cases for the case/control study. Controls (participants with *C. difficile* negative samples submitted during O1.1) would be recruited at a rate of 1:3, from the same participating centre. Where possible these will be age and gender matched. Given that we will only have a predefined group of participants to select from; it is possible that we are unable to completely match all controls, apart from at the geographical level. The same participants will be recruited for both case/controls studies (O1.3 and 1.4), using harmonised documentation (PIS, ICF and CRF).

#### 3.3.6 Data collection

Data will be collected via a standardised CRF, with a full supporting SOP. The CRF will be completed by the clinical care team at the participating site that submitted the sample (during O1.1). The CRF will not contain any participant identifiable data; all data will be held against a pseudoanonymised study code, with the link back held by the clinical care team only. COMBACTE-CDI investigators will not access participant's notes or access the link back. Once the CRF data has been collected and validated and verified the link-back will be destroyed by the local study site.

Data will be collected on the following variables to examine risk factors for CDI;

- Prior treatment with cytotoxic drugs
- Prior treatment with PPIs
- Underlying diagnoses
- Co-morbidities
- Previous antibiotics (preceding 12 weeks)
- Previous hospitalisation (preceding 12 weeks)
- Admission history (if an in-patient)
- Residential status (if in the community), e.g. home/nursing home
- Previous CDI
- Kissing contact with an infant
- Known contact with CDI case
- Previous wards/movement within hospital

#### 3.3.7 Data analysis

Odds ratios for different risk factors for CDI will be compared between settings (community/hospital) and countries. Risk factor comparison will also be made between different strain types (as identified in O1.2).

### 3.4 Transmission model (Objective 1.5)

#### 3.4.1 Study rationale

Consideration of patient movement in hospitals, LTCFs and the community is crucial in understanding the transmission dynamics and control of *C. difficile*. Data–driven estimates of CDI burden outside hospital settings are lacking (see 1.1). However, frequent interactions between hospital and LTCF populations mean their dynamics are inherently linked. Asymptomatic colonisation in LTCF is a potential reservoir for transmission; reported rates vary widely (4-50%), likely due to differences in healthcare system structures, and variations in definitions and long-term care case-mix. Overall, *C. difficile* transmission dynamics are poorly understood. Our molecular studies and statistical modelling have questioned the importance of symptomatic hospital patients, the traditionally assumed primary source of CDI acquisition

#### 3.4.2 Outcome measures

Primary outcome measure: A *C. difficile* transmission model describing the relatedness of each part of each target country's healthcare economy

Secondary outcome: A modelling tool that enables country and setting-specific CDI burden estimation and evaluation of intervention (cost-) effectiveness.

#### 3.4.3 Sampling Criteria for sample collection study (objective 1.5)

#### 3.4.3.1 Inclusion criteria

Data generated from the sample collection study and the case/controls studies described above.

*3.4.3.2 Exclusion criteria* None.

#### 3.4.4 Study methods

All CDI positive cases (as determined by the ECL), and a proportion of negative cases (at a ratio of 1 case to 3 controls) will have clinical data collected (after 6 months) on possible risk factors for CDI. Data will be compared to identify differences between countries and healthcare providers.

#### 3.4.5 Sample size

This is based on the collection of data from the previous objectives.

#### 3.4.6 Data collection

An anonimised dataset of the combined data from objectives 1.1-1.4 (as above) will be included in the transmission modelling. No additional data will be collected.

#### 3.4.7 Data analysis

We will use novel Markov chain Monte Carlo algorithms, to quantify transmission from different settings across different countries, using the repeated point-prevalence data collected in O1.1, along with the analysis on strain distribution (O1.2), impact on patient outcomes (O1.3) and risk factors (O1.4).

In addition, we aim to develop an innovative tool to enable country and setting-specific CDI burden estimation and evaluation of intervention (cost-)effectiveness. The model framework will be easily adaptable to different countries and settings. For example, so that settings of high antimicrobial use or CDI incidence can be simulated. The model could also provide a unique framework to perform

transmission dynamic model-based (cost-)effectiveness evaluations of interventions such as antimicrobial stewardship (e.g. targeting in- vs. outpatient prescribing) or admission screening

# 3.5 Surveillance study of current CDI detection, surveillance, treatment and attributable costs

#### 3.5.1 Study rationale

This part of COMBACTE-CDI (work-package 2) will highlight current guidelines for CDI diagnosis and treatment, at both European and national levels, and measure compliance with these. We will also measure the impact of CDI on healthcare systems, and determine if better compliance with guidelines leads to a lower burden in terms of reducing cases and costs. Objectives and deliverables for WP2 will be closely aligned with those for WP1, again using a synergistic approach to study design (see Figure 1). The timing of the objectives has been planned so that data and analyses generated from WP1 will be available for analyses in the required objectives in WP2. In addition, much of the analysis in the cost-effectiveness objective will be based on data generated from earlier objectives within WP2; the timing of these two objectives O2.5 and 2.6 has therefore been planned accordingly.

# *Highlight current guidelines for disease detection, notification and management/control Objective 2.1*

Five international societies have recently issued/updated guidelines on diagnosis, prevention, treatment and control of CDI.20,34-37 This reflects the increasing burden of CDI worldwide, new knowledge, and because some issues remain contentious. Underdiagnosis, as reported by our EUCLID study is a main contentious area. Underdiagnosis can depend on suboptimal laboratory testing for CDI and/or lack of suspicion by some clinicians, which could be overcome by automatic testing for CDI on every liquid stool sample. Overdiagnosis of CDI is also a challenge; it is important to distinguish CDI infection from colonization in hospitalised patients with diarrhoea.

One of the pillars of control of CDI is communication through reporting, but notification represents another conundrum not addressed by guidelines. In many countries, both in community and healthcare settings, there is mandatory notification for infectious diarrhoea, but not for CDI. In a recent systematic survey of clinical practice guidelines, showing that recommendations are often not consistent with available evidence, there is no mention of notification strategies for CDI.

# Determine the heterogeneity in testing density and in following the existing guidance on testing practices (objective 2.2)

We will aim to fill the current knowledge gaps about hospital identification of missed diagnoses (either due to lack of clinical suspicion or inadequate laboratory diagnostics). Existing programmes collecting European data on CDI testing heterogeneity are limited by either the number of hospitals surveyed per country or the number of countries. Also, current programmes focus on hospital acquired CDI; thus, data for the entire healthcare economy are lacking. More robust data comparisons could be made by expanding existing networks.

# Determine the heterogeneity in current surveillance practices and ways to improve them (objective 2.3)

An evaluation of changes in local laboratory CDI diagnostics in the period 2011-14 concluded that an increased use of 'optimal' diagnostics for CDI surveillance should be further promoted. Results of a

web-based electronic form sent to national coordinators showed that surveillance methods also varied considerably between countries. This illustrates the need for a harmonised European protocol to allow consistent monitoring of the epidemiology of CDI at European level. To support this further, a new CDI diagnostic guidance document has been published in 2016. We aim to determine the heterogeneity in current surveillance practices within the study source sites recruited for the prospective study in O1.1, and ways to improve them (by compiling and comparing information on the current surveillance systems at both European and country levels, and to determine the best strategy for future surveillance.

# Describe current treatment pathways for patients with CDI infection and recurrences (objective 2.4)

Current European treatment guidelines were published in 2014, but there are a paucity of data on national guidance and compliance with these guidelines. Guidelines often focus on in-patients and we will explore whether altered guidance is needed for different healthcare settings (see WP1). By building on networks used to establish variations in CDI diagnosis (EUCLID, LUCID, CLOSER), we will measure variability in treatment policies across Europe, focussing on the treatment/prevention of recurrent CDIs. By using the network of hospitals/laboratories established for the main study (O1.1.2), and their associated community practices, we will close the knowledge gaps within the community setting, with focus on long-term healthcare facilities. Comparisons will be made between healthcare locales/types and countries. Because information of outpatient costs of CDI are scarce, these new networks will also be used for further health-economic evaluations to analyse direct and indirect costs of patients with CDI outside hospitals (this data will feed in to O2.5 and 2.6).

Current guidelines on CDI treatment take into account both initial and recurrent episodes. For initial CDI treatment, pathways are mainly based on stratification on the severity of the disease; for recurrence, on the frequency of CDI episodes. The main concerns/knowledge gaps of these guidelines are represented by 1) heterogeneous definitions of severity  increasing rates of resistance to the often 1st-line treatment option metronidazole  lack of data on the risk of poorer outcomes in selected populations with CDI e.g. inflammatory bowel disease. Recently, Kanhafer *et al* demonstrated that the proportion of severe CDI cases varied widely (11-59%) depended on the definitions/risk factors used. This is important not only for stratifying patients for management strategies, including new treatments, but also for comparing data across studies. Some risk factors are also controversial; albumin levels could be the cause or effect of severe CDI. Studies should be addressed to better identify the role of these factors.

#### *Elucidate the overall costs of CDI, including management of multiples episodes and rehospitalisation (healthcare perspectives incl. indirect financial impact on the healthcare system). (Objective 2.5)*

There are current knowledge gaps regarding the costs of managing CDI in various healthcare settings. While some data exist on European tertiary care hospitals, the majority of CDI patients receive treatment in other hospital categories. Outside hospitals, little is known about costs in outpatients and nursing homes/LTCF. There are further knowledge gaps regarding costs of recurrent CDI.

#### 3.5.2 Outcome measures

This section of COMBACTE-CDI is surveillance of existing guidelines, including local knowledge and compliance. There is no fixed outcome measure for this.

#### 3.5.3 Sampling Criteria for surveillance studies (objectives 2.1-2.5)

#### 3.5.3.1 Inclusion criteria

All participating sites (hospital based), and their associated community healthcare providers who submitted samples on the sampling days (sample source sites). In four selected countries (representing the four zones of Europe) 10 nursing homes that did not submit samples on the sampling days will also be asked to complete the surveillance questionnaire, as there are a paucity of data on CDI regarding these facilities.

*3.5.3.2 Exclusion criteria* None

#### 3.5.4 Study methods

All included sites (see definition in inclusion criteria 3.5.3.1) will be asked to fill in a surveillance questionnaire asking about knowledge and compliance with current guidelines on CDI diagnosis, notification and control, surveillance, treatment and will collect attributable costs. Data will be compared to identify differences between countries and healthcare providers.

For cost data we will gather data on direct medical and non-medical costs of CDI in different healthcare settings to address the gaps and so elucidate the costs in all healthcare settings. Direct medical costs will include personnel (i.e. medical, nursing and technical service) as well as material costs (e.g. material and drug products). Direct non-medical costs will include for example, costs for carriage and expenditures of relatives

#### 3.5.5 Sample size

This is based on the number of participating sites (n = 120) and the number of associated community healthcare providers that submit samples on the sampling days, plus up to 40 nursing homes.

#### 3.5.6 Data collection

An online data capture system will be used to collect the data, built within the COMBACTE online network. This data will not contain any personal data, but details about individual sites knowledge and compliance with existing guidelines. Each site will have a unique anonymised study identifier for the online data capture system; investigators will therefore not be able to identify sites.

The main dataset will then be accessed via the online portal by the investigators for each of the objectives. Rule bases will be added to ensure that each objective investigator can only access data relevant to their objective.

#### 3.5.7 Data analysis

Comparisons of knowledge and compliance with guidelines for disease detection, notification and management/control will be made between countries and healthcare settings (community/hospital). Particular attention will be focussed on the dates of policies and the length of time it takes for European/national guidance to filter down to a local level. This may highlight a possible area for improvement in guideline communications.

Comparisons between testing policies and methodologies will be made between countries and healthcare settings (community/hospital). In addition, data from 1.1 on 'missed' case rates in these settings will allow identification of 'poor practice'.

Data will be compiled on current surveillance programmes for CDI and compliance with these, in different countries and settings. This will be used to determine a 'best-practice model' for surveillance and investigate mechanisms for increasing engagement with surveillance.

Comparisons of knowledge and compliance with guidelines for treatment pathways will be made between countries and healthcare settings (community/hospital). In particular comparisons will be made of risk stratification of patients (via severity criteria) between different healthcare settings and countries. Again this will be used to determine a 'best-practice model' for risk stratification.

We will aim to elucidate the overall costs in all healthcare settings. Data will be compared on the costs of CDI in different healthcare settings, and to address knowledge gaps regarding managing CDI outside hospitals, including in nursing homes. For the most comprehensive analyses on overall costs associated with CDI, a micro-costing approach will be combined with published data of the respective health systems for all health-economic evaluations. Additionally, by using data from Objective 1.3, indirect costs, i.e. productivity losses due to illness related disability and death before retirement age, in inpatient and outpatient settings will be addressed from societal perspectives to measure the full impact of CDI. The human capital and/or friction cost approaches will be used. All calculated costs will be expressed in an appropriate currency (e.g. EURO, €). Furthermore, discounting of all calculated costs will be performed by taking account of country and annual discount rates (normally 3% - 5% per year). Multivariate analyses will be performed to estimate relevant components of cost. Sensitivity analyses will be performed by using different annual discount rates.

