# 1.3 Study design of COMBACTE-CDI (overview)

To achieve our objectives, a large, complex study will be carried out (Figure 1), using proven methodology from a previous European wide (20 countries) CDI surveillance project (EUCLID network). In short, hospitals/laboratories of interest which carry out diagnostic testing of samples from both in-patients and community patients (including Long-Term Care Facilities patients) will be approached for inclusion. Hospitals/laboratories of interest will be selected to give respective coverage, based on population size, in the countries of interest and to represent North, South, East and West Europe.

Two study days will be selected, and all diarrhoeal stool samples received on those days by the hospital/laboratory in the study will be sent (regardless of age of patient or test requested) to the European Coordinating Laboratory (Leeds), where samples will be tested for CDI using the recommended 'optimal' testing methodology (ESCMID guidelines) (O1.1). Relevant ethical approvals will be sought (please see ethics section 1.4). Results will be compared to those from the submitting hospital/laboratory, including if the sample was even tested. Missed cases will be identified, enabling an estimation of the true burden of disease in both hospitals and the community. Isolates of *C. difficile* identified from the community and hospital samples will be sent for further analysis; including PCR-ribotyping, toxinotyping and whole genome sequencing to identify factors that may be driving clustering of strains (O1.2). Additional strains of animal and food origin collected from an existing network (NLZOH) will be added to the analysis for comparison between human and animal strains.

A clinical report form (CRF) will be designed to capture data for risk factor analysis and outcome data on all positive (ECL defined) and a proportion of CDI negative samples; completed 6 months after sample collection data (O 1.3 and 1.4). Please see section 1.4 for relevant ethical considerations.

All data collected from O1.1, 1.2, 1.3 and 1.4 will be brought into the analysis for transmission modelling in O1.5.

Hospitals/laboratories and their associated community practices will complete a surveillance questionnaire regarding:

- Testing policy and methodology;
- Surveillance practices;
- Guidelines available and compliance;
- The criteria for stratification of patients into 'severe' or 'non-severe' cases

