All these data will be uploaded (by the national coordinators) to a central website, thereby providing data for O2.1, 2.2, 2.3, 2.4

All of the data from the previous objectives in WP1 and WP2 will be fed in to the cost effectiveness analysis in O2.5 and 2.6

[figure not shown]

Figure 1. Schematic representation of study design (WP1 &WP2). A synergistic approach will enable completion of all the objectives from WP1 and WP2, with data created from a single, large complex study flowing into other objectives for further results analysis. Boxes in blue denote objectives in WP1, and those in orange denote for objectives in WP2. Due to the inter-related nature of the objectives within both WP1 and WP2, the flow of work has been planned to ensure maximum outputs within the timeframe of the grant. The directions of the arrows indicates data flow and, therefore, also the timing of activities;. i.e. Strains cannot be analysed (1.2) until after they have been collected (1.1). This ambitious comprehensive project design takes influence from several

existing, separate studies; the scope of producing all of these is data from one, well-designed and far-reaching study is novel and innovative.

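### A comparison of which severity criteria sites use is to yield a best-practice model for risk stratification, with no selection criterion and no patient outcome among the stated inputs

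*Protocol*

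**What the plan says.** Protocol section 1.3 lists the content of the site questionnaire, including "The criteria for stratification of patients into 'severe' or 'non-severe' cases". The uploaded answers are described as "thereby providing data for O2.1, 2.2, 2.3, 2.4". Objective 2.4, on treatment pathways, is therefore fed by this questionnaire. Section 3.5.6 describes the dataset: "This data will not contain any personal data, but details about individual sites knowledge and compliance with existing guidelines". The same section restricts each investigator to the data for their own objective.

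Section 3.5.2, on outcome measures for this part of the study, says: "There is no fixed outcome measure for this".

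Section 3.5.7 gives the analysis: "In particular comparisons will be made of risk stratification of patients (via severity criteria) between different healthcare settings and countries". The next sentence gives its use: "Again this will be used to determine a 'best-practice model' for risk stratification".

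The rationale for objective 2.4 in section 3.5.1 cites a study that "demonstrated that the proportion of severe CDI cases varied widely (11-59%) depended on the definitions/risk factors used". It calls some risk factors controversial and says their role still needs to be identified.

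Outcome data are collected in the case/control study. Protocol section 3.2.6 lists "Outcome 30 days and 6 months after the sample (discharged, in-patient, died") on the same form as the severity markers.

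**The concern.** Whether a severity definition is good practice depends at least partly on whether the patients it labels severe do worse than the others. A table of which criteria are used, by country and setting, contains no information on that. It would look the same whether or not a given definition predicts death.

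The protocol gives reasons why this matters: definitions disagree widely, and the rationale says severity affects both how patients are stratified and how studies are compared. A definition put forward as best practice across Europe would carry weight with guideline groups. On the text as written, nothing in the analysis would show whether that weight is deserved.

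**Working it through.** **Step 1. Trace the inputs.** The plan states no figure for this point, so there is none to reproduce. The check is of what enters the best-practice model.

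| Output in section 3.5.7 | Stated inputs | Work-package 1 data named? |
|---|---|---|
| Poor practice in testing | Testing policies and methods, by country and setting | Yes: missed-case rates from objective 1.1 |
| Indirect costs | Costing data | Yes: objective 1.3 |
| Best-practice model for risk stratification | Reported severity criteria, knowledge and compliance, by country and setting | No |

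The authors name a link to patient-level data where they intend one. For risk stratification they name none.

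**Step 2. Look for the analysis elsewhere.** Protocol section 3.2.7 compares outcomes by setting, country and strain type. SAP sections 7.2 and 7.3 compare cases with controls and model case/control status. None relates a severity marker to death or escalation within cases.

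**Step 3. Check that the data exist.** SAP Appendix 1 has recorded severity grade (4.5.1), temperature, creatinine, white cell count and albumin (5.1-5.4), colitis (5.12), medical and surgical escalation (7.1, 7.2) and death (10.5, 10.7). Definitions reported in the questionnaires could be applied to these records without new collection.

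**Step 4. Size what a linked analysis could show.** SAP Table 1 gives 103 CCNA-positive and 71 Simoa-only cases: 103 + 71 = 174 toxin-positive. Adding 39 toxin-negative cases gives 213. The documents give no mortality rate, so 5%, 10% and 15% are assumed.

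Deaths = N × mortality: 174 × 0.05 = 8.7; 213 × 0.15 = 32.0. The range is about 9-32.

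Detectable risk ratio (RR), severe against non-severe, at two-sided 5% and 80% power. With severe share s and mortality m, risk in the non-severe is p0 = m / (s·RR + 1 − s), and in the severe p1 = RR·p0. Example, N = 174, s = 0.11, m = 0.10: RR = 4.15 gives p0 = 0.10/1.3465 = 0.074 and p1 = 0.308, which just reaches 80% power.

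| N | Severe share | m = 5% | m = 10% | m = 15% |
|---|---|---|---|---|
| 174 | 11% | 7.15 | 4.15 | 3.25 |
| 174 | 59% | none below 40 | 5.7 | 3.45 |
| 213 | 11% | 6.1 | 3.75 | 2.95 |
| 213 | 59% | 34.75 | 4.4 | 2.95 |

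The normal approximation is rough with so few deaths, but the message is clear: risk ratios of about 3 or more.

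**Step 5. Precision of discrimination.** For a binary definition, AUC = (sensitivity + specificity)/2. The Hanley-McNeil approximation gives, for AUC A with d deaths and n survivors, SE² = [A(1−A) + (d−1)(Q1−A²) + (n−1)(Q2−A²)]/(d·n), with Q1 = A/(2−A) and Q2 = 2A²/(1+A). At A = 0.70, Q1 = 0.538 and Q2 = 0.576. For N = 174 and m = 10%, d = 17.4 and n = 156.6: SE² = 14.46/2724.8, so SE = 0.073 and the 95% interval is 0.56 to 0.84. Over m = 5-15%, SE is 0.101-0.060 for N = 174 and 0.092-0.055 for N = 213. At 8.7 deaths the interval is 0.70 ± 1.96 × 0.101, or about 0.50 to 0.90, which barely excludes no discrimination, if at all.

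**Step 6. Chance of picking the right definition.** Simulation assumptions: four independent definitions labelling 11%, 27%, 43% and 59% severe; one prognostic with odds ratio 3-6; mortality 5-15%; the largest AUC chosen. Correct selection is about 49-99% for N = 174 and 55-100% for N = 213. The low end is the case where the 11% definition is the prognostic one. Repeat runs move that floor by a few points.

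**The case against.** A reader might infer that the plan will crown the most-used criterion, or that it is certain to name a definition even if none predicts outcome. The documents do not support that. Section 3.5.7 gives no selection rule of any kind, so no probability of a wrong choice can be attached to it. The fault is an undefined term resting on data that cannot support it.

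A reader might also infer that patient outcomes are excluded from objective 2.4. That goes too far. Protocol sections 1.2.2 and 3.5.1 say work-package 1 data will be available for the work-package 2 objectives that require them. Figure 1, which shows data flow, is not visible here, so a link from objective 1.3 to 2.4 cannot be ruled out. The supplied SAP covers only the case/control study, so its silence is weak evidence. What can be said is that the text states no such link, and an arrow would not specify an analysis. Objective 2.6 compares pathways on cost and is not said to validate severity criteria.

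On scope, objective 2.4 is to describe pathways, and best practice could mean harmonised or guideline-concordant practice, as in the parallel surveillance model. That is a fair reading and no prognostic validation was promised. It supports calling the comparison descriptive; it does not support an undefined best-practice label.

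The strongest objection concerns the remedy, and it stands as a limit:
- Deaths will be few, and 174 and 213 are maxima.
- Of the 174, 20 + 22 = 42 are community patients, for whom laboratory markers may more often be missing.
- Real definitions share markers, so telling them apart will be harder than with independent definitions.
- Patients are treated, possibly according to severity, so death is a confounded yardstick.
- Choosing the largest AUC always names a winner, so the added analysis needs its own condition for declaring none.

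**Conclusion.** The point holds as a gap between a planned conclusion and its stated evidence. A between-site comparison of severity criteria describes practice and cannot show which definition identifies patients who do badly. The plan promises a best-practice model from it, gives no selection criterion and names no outcome, while the needed data are collected on the same cases without a planned analysis.

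The gain available is limited. With about 9-32 deaths, a linked analysis could distinguish only strong criteria and may end without a preferred definition. This rests on assumed mortality of 5-15% and full recruitment with complete markers. No primary outcome of the study is affected. The grade is a cheap improvement. Which severity criterion is right is not judged.

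**What to change.** In Protocol section 3.5.7, state that the comparison of severity criteria between countries and settings is descriptive. Then add to the plan, in substance:

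- Each severity definition reported in the questionnaires that can be derived from the CRF (temperature, creatinine, white cell count, albumin, colitis) is applied to all toxin-positive cases (CCNA or Simoa), with all 213 cases as a secondary set.
- Sensitivity, specificity and AUC are reported for 30-day all-cause death, and for death or surgical escalation, with 95% intervals that allow for clustering by site.
- Missingness of each marker is reported, by setting.
- The term best practice is used only if the intervals exclude no discrimination and separate the definitions. Otherwise the report says that no definition is clearly better.
- Two limits are stated: the expected number of deaths, and possible confounding by severity-guided treatment.

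The minimum alternative is to call the comparison descriptive and drop the best-practice wording.

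The cost is a change of wording and one small analysis on data already collected. The drawback is wide intervals and a real chance of an inconclusive result.
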